Sensitivity (the proportion of patients correctly diagnosed with OSA) and specificity (the proportion of patients correctly rejected as having OSA) values of sleep scores will be computed, and the area under the receiving operating characteristic (ROC) curve will also be calculated. A sensitivity value of .825 will be considered clinically significant. Pearson correlation will be used to identify the association between OSA and PSG AHI diagnoses. Bland and Altman plots will be generated to demonstrate the degree of identity between the outcomes of the Belun Rung and PSG AHI diagnostic methods.

Additional data such as sleep parameters, stress parameters, and total sleep time will be reported as descriptive analyses (e.g., means and standard deviations).

The primary study endpoint is to investigate the accuracy, sensitivity, and specificity of the Belun Ring in assessing obstructive sleep apnea (OSA) when compared to the gold standard which is polysomnography (PSG). The secondary endpoint is to evaluate the tolerability of the device by the patients.

Confidentiality of Specimens and Banking

Are you storing the specimen(s) for future use for other research projects?

- I am not collecting specimens in this research project
- I am **not** storing specimens in this research project
- □ Yes
- 🛛 No

Confidentiality of Data

- 1. To maintain the confidentiality of the data:
- ☑ I will use a unique study identifier (not derived from the participants' personal identifiers) to code individuals' data and I will store this ID log separate from study data.
- □ Other *(please explain)*:
- 2. How are you storing your electronic data?
 - ⊠ UH Redcap
 - □ CWRU Redcap
 - CWRU's SRE (Secure Research Environment)
 - □ CWRU Box
 - \Box OnCore
 - □ UH Secure Network Drive
 - □ CWRU Secure Network Drive

☑ Other Belun Technology Company will provide 3 HIPAA-compliant laptops free of charge during the entire duration of the research trial. Each sleep laboratory will have 1 HIPAA-compliant laptop from Belun Technology Company which will be used to assign and prime a specific Belun Ring device to a specific subject. All these 3 laptops are HIPAA-compliant and have been approved by UH Research IT prior start of the study. Before the night of the scheduled polysomnography (PSG), the sleep technician will get an email from the study team regarding list of patients who will participate in the study as well as the each patient's corresponding unique identifier. *On the night of the polysomnography (PSG), the sleep technician will use the unique* patient identifier to identify the subject in the Belun Ring and use the same unique identifier when uploading data from Belun Ring to HIPAA-compliant laptop the following after completion of the polysomnography (PSG). The study coordinators will transfer all data from the Belun Ring HIPAA-compliant laptop to the UH Redcap data collection sheet. After updating UH Redcap data collection sheets, the study coordinators will delete data from the Belun Ring device and the HIPAA-compliant *laptop. During the study, no data will be shared with Belun Technology Company* and the latter will not access their laptops until the study is completed. After the study is completed, all the Belun Ring devices and the 3 HIPAA-compliant laptops from Belun Technology Company will be returned to Belun Technology Company. Any lost or damaged Belun Ring device or laptop will not be the financial responsibility of UH nor the patient.

WESTERN	University	Sparta IRB	HRP-503BIO	TEMPLATE: Biom	edical Protocol	
RESERVE	Hospitals	Research Tracking + Administration	Approved:		Prior Version:	08/16/2018

3. I acknowledge that paper research data and documents will be stored in a double-locked secure environment in the following location:

Location: \boxtimes Office of [name] and Bolwell-6th floor sleep lab at the Department of Pulmonary, Critical Care, and Sleep Medicine at [name]

- 4. Will data be shared?
- \square N/A
- 🛛 No

□ Yes

1. List the exact data elements that will be shared:

1.

2. Describe how data will be sent: (Please note: if sharing data, please contact your Grants and Contracts Specialist to ensure the proper contracts are in place.)

HIPAA Authorization

If you are going to be accessing PHI (Protected Health Information), indicate how HIPAA authorization will be obtained (check all that apply):

- $\boxtimes\ HIPAA$ authorization is in the consent form
- ☑ Requesting a full or partial waiver of HIPAA for prescreening
- □ Requesting a full or partial waiver of HIPAA
- 1. Describe why the study cannot be completed without the specified identifiable information.

We will need to do chart review if there is not enough information about the patient's comorbid conditions. Also, one of the exclusion criteria in this research is involvement of potential subject in another investigational study or recent hospitalization in the last 30 days.

- 2. If the identifiable information will be used or disclosed by anyone other than the research team, please state who those individuals/entities are and provide justification for the disclosure.
 - \boxtimes Identifiable information will **not** be used or disclosed by anyone other than the research team
 - \Box Identifiable information will be used or disclosed to:
- 3. Describe how long identifiers will be kept for in relation to study length and data collection and analysis.

Research data will be stored for at least 3 years following study closure or the required length of time required by applicable regulations at that time; whichever is longer.

I assure that protected health information collected for purposes of this research study will not be reused or disclosed to any other person or entity, except as required by law, for

authorized oversight of the research study, or for other research for which the use of disclosure of protected health information for which an authorization or opportunity to agree or object is not required by 45 CFR 164.512

Risks to Research Participants

- 1. List the reasonably foreseeable risks such as breach of confidentiality, discomforts, hazards, or inconveniences to the research participants related to their participation in the research. Include a description of the probability, magnitude, duration, and reversibility of the risks. Include the physical psychological, social, legal, and economic risks.
 - a. Risk of breach of confidentiality is prevented by using computers within UH campus and laptops owned by UH as these computers and laptops are encrypted and secured. No transferring of data using USB or text messages will be allowed. Communication between the principal investigator, mentor, and members of the research team will be done through UH-encrypted email or in person in either [name] office or the conference room in Department of Pulmonary, Critical Care, and Sleep Medicine which are both located on the 6th floor of Bolwell building in University Hospitals- CMC.
 - b. The sensor can be warm to touch occasionally but not hot enough to cause burn.
 - c. The clip-on sensors may cause some pressure discomfort if the wrong size was applied. The patient may alert the technician so patient can be fitted another size of the Belun Ring.
- 2. If applicable, indicate which experimental procedures may have risks to the research participants that are currently unforeseeable. \boxtimes N/A
- 3. If applicable, describe the risks to others who are not research participants. \bowtie N/A
- 4. Describe the availability of medical or psychological resources that research participants might need.
 - ⊠ N/A

Additional Considerations for Pregnant Women:

- 5. Indicate which procedures may have risks to an embryo or fetus should the research participant or their partner be or become pregnant.
 - ⊠ N/A However, the Belun Ring has not been tested in children or pregnant women.
 - □ Each individual providing consent is fully informed regarding the reasonably foreseeable impact of the research on the fetus or neonate.
 - □ No inducements, monetary or otherwise, will be offered to terminate a pregnancy.
 - □ Individuals engaged in the research will have no part in any decisions as to the timing, method, or procedures used to terminate a pregnancy.
 - □ Individuals engaged in the research will have no part in determining the viability of a neonate.

Provisions to Protect the Privacy Interests of Research Participants

The sleep study will be done in separate rooms in the sleep lab. Privacy will be protected with doors closed.

Potential Benefit to Research Participants

Sparta IRB

University Hospitals

□ There is potential benefit to research participants.

- *1*. Describe the potential benefits that individual research participants may experience from taking part in the research. Include the probability, magnitude, and duration of the potential benefits.
- \boxtimes There is **no** direct benefit to research participants.
 - 2. If no direct benefit, state the potential benefit to society or others. *Do not list compensation.*

If the study showed that Belun Ring has high sensitivity and specificity when compared to the gold standard which is the polysomnography (PSG), it can be used as a simple, safe, and inexpensive alternative test to in-lab polysomnography (PSG) testing or as a screening tool prior in-lab polysomnography (PSG) testing. As the device costs less than 10% of a typical home sleep testing device and 1% of an in-lab testing software, its use may revolutionize how obstructive sleep apnea (OSA) is evaluated.

Withdrawal of Research Participants

🛛 N/A

If a participant did not sleep for at least 4 hours during the sleep study, patient will be withdrawn from the research without their consent. Nothing needs to be done in such situation as no follow up is needed.

Alternatives to Participation

 \boxtimes The alternative is for research subjects not to participate.

If patient wishes not to participate, patient will still get the standard overnight in-laboratory polysomnography (PSG) ordered by his or her physician. There will be no change of care regardless.

Costs to Research Participants

 \boxtimes There are no costs to research participants or their insurance companies (there are no clinical visits or billable procedures).

Research Participant Compensation

- \boxtimes There is **no** compensation or reimbursement for research participants.
- \Box There is compensation for research participants.

Describe the schedule, payment method, and payment total of any incentives or compensation that research participants will receive for participation in the research (e.g., gift cards or cash with amount, t-shirts, devices, bags, swag, etc.)

□ There will be reimbursement for research participants. Describe the schedule, payment method, and payment total of any reimbursement that research participants will receive for participation in the research (e.g., gift cards or cash with amount, etc.)

Compensation for Research Related Injury

Describe who will pay for the costs of medical treatment and/or compensation in the event of a research related injury:

- $\Box\,$ Funding agency is providing some/all payment for injury
- \boxtimes Funding agency is providing no payment for injury
- \square N/A

Provisions to Monitor the Data to Ensure the Safety of Research Participants

1. Describe how often the data will be monitored for completeness, accuracy and adherence to the protocol.

The principal investigator, the mentor, the research coordinator, and the study coordinators will be monitoring data for completeness, accuracy, and adherence to protocol at least 3 times a week. The PI will discuss any discrepancies with the individual that collected the data for prompt resolution.

- 2. Indicate if there will be a Data and Safety Monitoring Board or Committee:
- ☑ There will not be a formal Data and Safety Monitoring Board/Committee.

☐ There will be a formal Data and Safety Monitoring Board/Committee. Provide information about the DSMB/C including the contact information of the committee member(s) (as applicable); whether it is independent from the study sponsor; how often it meets; the type of data that will be used; written reports, etc.

Drugs or Devices

□ This is not a drug or device study. The protocol is considered non-therapeutic (non-therapeutic is defined as research not intended to diagnose, prevent, cure, mitigate, treat, etc. a disease or condition) by the FDA. – *You may delete the rest of this section*.

OR

- ☑ This is a drug or device study. The protocol is considered therapeutic (research intended to diagnose, prevent, cure, mitigate, treat a disease or condition) by the FDA.
- 1. Is there an active IND (Investigational New Drug) or IDE (Investigational Device Exemption) for the proposed clinical research study?
 - □ Yes, provide an official letter of support or proof of approval which identifies the IND/IDE holder and IND/IDE number. *Please attach this in the SpartaIRB smartform*
 - \boxtimes No, see question below:
- 2. Is the drug IND exempt *OR* is the device (and its use) a non-significant risk device for the proposed study design?

Yes, please identify the authorized party who made the determination and provide supporting documentation as applicable.

FDA approved the device on May 29, 2018.

- □ No *NOTE:* either an active *IND/IDE* or an exemption would be required for investigational product use in a therapeutic protocol.
- \square N/A
- 3. If the research involves drug(s) or device(s), describe your plans to store, handle, administer and track those drug(s) or device(s) to ensure that they will be used only on research participants and be used only by authorized investigators.

Each Sleep laboratory will have up to 8 devices of different sizes. Each device has its own cover and docking cradle and will be cleaned with alcohol thoroughly after each use.

Additional Information

N/A

Community-Based Participatory Research

- \boxtimes This is not a community-based participatory research project *please leave the rest of this section blank*
- □ This is a community-based participatory research project Describe the involvement of the community in the design and conduct of the research.

Note: Community based research is research that is conducted as an equal partnership between academic investigators and members of a community. In Community Based Participatory Research (CBPR) protects, the community participates fully in all aspects of the research process.

International information

 \boxtimes This is **not** an international study.

MULTI-SITE RESEARCH (when UH or CWRU is the IRB of Record)

Does this project have multiple sites?

□ Yes

 \boxtimes **No** – please leave the rest of this section blank

Non-Local Site Information for Multi-Site Studies

If this is a multi-site study where you are the lead investigator, list the following information for each relying site:

- 1. Name of site:
- 2. PI of relying site:
- 3. Name of IRB contact:
- 4. Phone number of IRB contact:
- 5. Email address of IRB contact:

Non-Local Recruitment Methods for Multi-Site Studies

Sparta IRB

University Hospitals

If this is a multi-site study and research participants will be recruited by methods not under the control of the local site (e.g. call centers, national advertisements) describe those methods. Local recruitment methods are described above.

- 1. Describe when, where, and how potential research participants will be recruited.
- Describe the methods that will be used to identify potential research participants.
- Describe the materials that will be used to recruit research participants.

Multi-Site Research Communication Plan (when you are the lead investigator)

If this is a multi-site study where you are the lead investigator, describe the processes to ensure communication among sites including:

- □ *All sites will have the most current version of the protocol, consent document, and HIPAA authorization*
- □ All required approvals (initial, continuing review and modifications) have been obtained at each site (including approval by the site's IRB of record)

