Belun Technology Company has conducted two studies in 2017-2018 and has published an abstract of their preliminary findings from Hong Kong at the 2018 APSS meeting. This validation study was conducted in Prince of Wales Hospital in Hong Kong using the original version of the Belun Ring which had no capability of detecting total sleep time (TST). This study excluded patients with a history of congestive heart failure (CHF), stroke, chronic obstructive pulmonary disease (COPD), neuromuscular disorder, or hypoventilation well as those on beta-blockers and calcium blockers. In-lab polysomnography (PSG) signals were recorded simultaneously with device under test and the reference apnea-hypopnea index (AHI) values were manually scored by certified sleep technician according to the American Academy of Sleep Medicine (AASM) Manual for the scoring of Sleep and Associated Events version 2.3. A total of 23 Chinese subjects (17 males, 6 females; 53.2 ± 11.8 years old) were enrolled in the validation and each subject contributed one record of overnight measurement. The time of sleep period was 352.1 ± 47.5 minutes and the distribution of the reference apnea-hypopnea index (AHI) was from 4.1 to 98.3 (38.5 ± 28.3) /hour. The correlation between reference apnea-hypopnea index (AHI) and Sleep Score is r = 0.977 (P<0.001). It was concluded that the overall sensitivity and specificity for the classification of severity of obstructive sleep apnea (OSA) are good, especially in moderate and severe groups. In the subsequent Colorado study (unpublished data), a newer version of Belun Ring with the capability of measuring total sleep time (TST) was used. The correlation between reference PSG-AHI and Belun Ring REI is r = 0.865 using an AHI cutoff of 15 and the overall accuracy was 84.4% with a sensitivity of 80% and a specificity of 88%. The Belun Ring-estimated total sleep time (TST) correlates well with the polysomnography (PSG)-derived total sleep time (TST) with an r = 0.950. In this study, the new version Belun Ring pulse oximeter will be used for evaluation which will be compared with the standard attended in-lab PSG in order to determine the accuracy, sensitivity, and specificity of Belun Ring as an outpatient evaluation for obstructive sleep apnea (OSA).

1 13

usion and Exclusion Criteria
Inclusion Criteria
All adult patients age 18-80 years old scheduled for overnight in-lab sleep study
Provision of signed and dated informed consent form
Exclusion Criteria

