Recent hospitalization in the past 30 days
Patients on home oxygen, non-invasive ventilator, diaphragmatic pacing, or any
form of nerve stimulator
Patients with pacemaker, defibrillator, left ventricular assist device (LVAD), or
status post cardiac transplantation
Patients with baseline heart rate under 50 bpm or over 100 bpm during last clinic
visit or prior to study at the sleep lab
Patients with unstable cardiopulmonary status judged to be unsafe for sleep study
by the sleep tech and/or the on-call sleep physician in the sleep lab on the night of
the study

- 6. Patients who are unable to complete the required study
- 7. *Patients involved in another investigational study*
- 8. Pregnant women

Number of Research Participants

We will enroll at least 80 subjects in two UH sleep laboratories.

Vulnerable Populations

- 1. Indicate specifically if you will include each of the following special populations by checking the appropriate box:
 - □ Adults unable to consent
 - □ Minors (infants, children, teenagers)
 - \Box Wards of the state
 - □ Foster Children
 - Pregnant Women
 - □ Neonates
 - □ Neonates of Uncertain Viability
 - ⊠ Employees of CWRU or UHHS
 - □ Prisoners
 - ⊠ Illiterate Individuals
 - \boxtimes Non-English Speaking
 - ⊠ University Students
 - □ None
- 2. If excluding pregnant women, illiterate or non-English speaking individuals, provide a scientific rationale for the exclusion. Inconvenience or cost is not an acceptable rationale. *There is unknown risks and benefits of the device to the growing fetus; hence pregnant women are excluded in this study.*
- 3. If the research involves individuals that are included in a vulnerable population, describe the additional safeguards included to protect the rights and welfare of the individuals for each population indicated.

The illiterate individuals are not excluded as long as they make a mark or able to sign their name in the written informed consent form. Also, the written informed consent form will be read to them verbatim before they give their consent.

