Non-sleep providers and sleep providers in UH will order polysomnography as they see patients in their respective clinics. Our schedulers in UH Bolwell Building will call and schedule these patients for the standard, overnight, attended, in-lab sleep study, also known as polysomnography. Subsequently and routinely, the schedulers will e-mail a packet of general information to these patients and add the email recruitment form for the Belun Ring Study. On the email recruitment form itself, there is a phone number and email address for patients to call or e-mail if they are interested or if they decide to opt out. If the research team did not hear anything from the patient after 14 days of emailing the recruitment form, the study coordinators will look up the names of the patients in Enterprise software and make follow-up calls on the patients to ask them if they are interested in participating in the research. Prior making follow-up calls, the study coordinators will do a simple chart review using UH Ambulatory Care EMR to screen patients for eligibility and collect demographics data. If a certain patient is found to be eligible, the study coordinators will call that patient using the phone recruitment script and discuss the Belun Ring Study in detail. The study coordinators will also use this phone interview as a time to answer patient's questions and verify patient's eligibility, in case there are unclear information noted during chart review. If patient is eligible and agreed to participate in the research during the phone interview, the patient's name and related personal information will be placed in the linking sheet and a unique identifier will be assigned to that patient.

- 3. Describe the source (e.g., from what department, EMR, etc.) of the research participants. Enterprise software of the UH Sleep Laboratory is the master schedule where we can see the list of patients scheduled for overnight attended in-laboratory sleep study, also known as polysomnography in the 2 sleep laboratories of University Hospitals namely in Bolwell and Beachwood locations.
- 4. Describe the methods that will be used to **identify** potential research participants. Chart review of the patients listed from the Sleep Lab master schedule will also be done to identify which patient meets eligibility criteria. We will use UH Ambulatory Care for the EMR to do chart review.

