This prospective, single-blind, non-randomized, single-visit study will recruit at least 80 patients who are suspected to have obstructive sleep apnea (OSA) and are scheduled to undergo polysomnography (PSG) in a sleep laboratory for evaluation of obstructive sleep apnea. Patient recruitment starts with e-mailing recruitment forms to the patients who have been scheduled for polysomnography. On the email recruitment form itself, there is a phone number and e-mail address for patients to call or e-mail if they are interested or if they decide to opt out. If the research team did not hear anything from the patients after 14 days of emailing the recruitment forms, the study coordinators will look up the names of the patients in Enterprise software which is the master schedule for all patients going for overnight in-lab polysomnography. Subsequently, the study coordinators will do a simple chart review using UH Ambulatory Care EMR to screen patients for eligibility and collect demographics data. If a certain patient is found eligible, one of our research team will make follow-up call to that patient and determine if patient is interested in participating in the research. During this phone interview, the phone recruitment script will be used to verify the subject's eligibility criteria, discuss the Belun Ring study further, and answer all the patient's questions. If patient is eligible and agreed to participate in the research during the phone interview, the patient's name and related personal information will be placed in the linking sheet and a unique identifier will be assigned to that patient. Then, the list of patient's unique identifier will be e-mailed to the sleep technician prior to the scheduled sleep study. All communication with the sleep technician will be done through UH e-mail addresses within UH premises. On the other hand, if the patient got the e-mail and called the research team to opt out in the trial, that patient will be not be called and no chart review will be done in the EMR for that patient.

On the night of the scheduled polysomnography (PSG), Sleep Questionnaire and 2 copies of the written informed consent will be presented to the patient together with other routine care pre-sleep questionnaires. The Sleep Questionnaire will be completed by the patient prior the start of the polysomnography. Our CREC certified sleep technicians will discuss the consent form in detail

	Sparta IRB	HRP-503BIO	TEMPLATE: Biom	edical Protocol	

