 - \boxtimes Medical record number
 - □ Health plan beneficiary number
 - □ Account number
 - □ Certificate/license number
 - \Box Any vehicle or other device serial
 - □ Device identifiers or serial numbers
 - \Box Web URL
 - □ Internet protocol (IP) address
 - \Box Finger or voice prints
 - □ Photographic images
 - Other: *Sleep study recording data*
- 2. List all other data to be collected for the research study (e.g. laboratory values, physician notes, length of stay, etc.)
 - a. Age, gender, race, weight, height, and BMI
 - b. Past medical and surgical histories
 - c. Concomitant medications
 - d. Physicians' notes on clinic visits for chart review to check subject eligibility

WESTERN	University	Sparta IRB	HRP-503BIO	TEMPLATE: Biom	edical Protocol	
RESERVE	Hospitals	Research Tracking + Administration	Approved:		Prior Version:	08/16/2018

- e. Previous polysomnography (PSG) and home sleep apnea test (HST) in the past
- *f.* All subjective information related to current sleep problem including current CPAP use
- g. SP21256 Sleep Questionnaire
- h. STOP-BANG score
- *i.* UH Pre-sleep Questionnaire part of routine care prior doing the standard polysomnography (PSG)
- *j.* UH Post-Sleep Questionnaire part of routine care after doing the standard polysomnography (PSG)
- *k.* Patient satisfaction survey part of routine care after doing the standard polysomnography (PSG)
- *l.* Arterial blood gas and bicarbonate values if available
- m. Echocardiogram or cardiac MRI results if needed
- n. Total sleep time, Sleep latency, SpO2 nadir, oxygen desaturation index (ODI) and overall apnea-hypopnea index (AHI) in the polysomnography (PSG) during the testing
- o. Total sleep time, SpO2 nadir, and respiratory event index (REI) in the Belun Ring device during the testing

Data Analysis Plan

RStudio Version 1.1.456 will be used to perform an a priori power analysis for the sensitivity of the Belun Ring REI and PSG AHI diagnoses. At alpha = 0.05, power = 0.95, minimum acceptable sensitivity = 0.825, target level of sensitivity = 0.977, a minimum of 35 obstructive sleep apnea (OSA)-positive patients is required. With an estimated 80% of patients receiving a positive polysomnography (PSG) diagnosis of obstructive sleep apnea, recruitment of 42 patients at minimum is necessary. Because not all recruited patients may complete the overnight PSG, we plan to collect data from approximately 50 patients.

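### The inclusion criterion is wider than the suspected-OSA population the study describes, and nothing keeps nights recorded on positive airway pressure out of the accuracy analysis

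*Combined protocol and SAP*

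**What the plan says.** Apart from signed consent, the only inclusion criterion under Inclusion and Exclusion Criteria is "All adult patients age 18-80 years old scheduled for overnight in-lab sleep study". It does not mention suspected OSA, a diagnostic purpose or an untreated night.

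Study Design is narrower: "This prospective, single-blind, non-randomized, single-visit study will recruit at least 80 patients who are suspected to have obstructive sleep apnea (OSA"), and the night is one on which they are "scheduled to undergo polysomnography (PSG) in a sleep laboratory for evaluation of obstructive sleep apnea". The protocol title likewise speaks of patients referred for assessment of OSA.

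The nearest of the eight exclusions begins "Patients on home oxygen, non-invasive ventilator, diaphragmatic pacing". It does not define non-invasive ventilator to include CPAP, and no exclusion mentions CPAP, a treated night or an existing OSA diagnosis.

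Recruitment Methods says how the criteria are applied: "Chart review of the patients listed from the Sleep Lab master schedule will also be done to identify which patient meets eligibility criteria".

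The List of Data to be Collected includes "All subjective information related to current sleep problem including current CPAP use" and "Previous polysomnography (PSG) and home sleep apnea test (HST) in the past". No section says that the study night is recorded without positive airway pressure, or how a night with it would be analysed.

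**The concern.** Coordinators screen the master schedule against the eligibility list, so the list decides who enters. A coordinator following it has no stated ground for turning away a patient with known OSA who is booked for a night on treatment.

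The aim is the accuracy, sensitivity and specificity of the ring for evaluating OSA. On a treated night the AHI measures the events that remain on therapy, not whether the patient has OSA. A known OSA patient can then be counted among the PSG-negatives. Three things follow:

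- Specificity would rest partly on people whose OSA is suppressed rather than absent.
- The mix behind the ROC curve, the correlation and the Bland-Altman plot would change.
- The 80% positive rate behind the sample size would no longer describe the enrolled group.

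**Working it through.** **Inputs from the Data Analysis Plan.** Alpha 0.05 (sidedness not stated), power 0.95, minimum sensitivity 0.825, target sensitivity 0.977, 35 OSA-positive patients required, 80% assumed PSG-positive, about 50 patients planned. Number of Research Participants and Study Design instead give at least 80 patients.

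**Assumptions, not in the documents.** t is the share of enrolled nights on treatment. q is the share of treated nights that still score PSG-positive. The 80% is taken to apply to untreated nights.

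**The plan's own figure.** The arcsine formula with a one-sided test gives effect size h = 2(arcsin √0.977 − arcsin √0.825) = 0.5587. Then n = ((1.645 + 1.645)/0.5587)² = 34.7, rounded up to 35. The stated 35 reproduces. By the exact binomial, 35 positives (success at 33 or more correct) has power 95.4%.

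**Expected positives.** These are N × [0.80(1 − t) + q·t]. The lower value in each cell has all treated nights negative (q = 0); the higher has 40% of them still positive.

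| t | N = 50 | N = 80 |
|---|---|---|
| 0 | 40 | 64 |
| 10% | 36 to 38 | 57.6 to 60.8 |
| 20% | 32 to 36 | 51.2 to 57.6 |
| 30% | 28 to 34 | 44.8 to 54.4 |
| 50% | 20 to 30 | 32 to 48 |

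**Where 35 is lost, with q = 0.** Solve N × 0.80(1 − t) = 35:

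- N = 50: t = 1 − 35/40 = 12.5%.
- N = 80: t = 1 − 35/64 = 45.3%.

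With q = 0.40 the limit at N = 50 rises to (0.80 − 0.70)/(0.80 − 0.40) = 25%.

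**Power at the larger target.** With N = 80, t = 20% and q = 0, 51 positives (success at 47 or more correct) give exact power 99%. At t = 30%, 44 positives give 98%.

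**Case mix, which does not depend on N.** The fraction of PSG-negatives that are treated nights is (1 − q)t / [(1 − q)t + 0.20(1 − t)].

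- q = 0, t = 10%: 0.10/(0.10 + 0.18) = 36%.
- q = 0, t = 20%: 0.20/(0.20 + 0.16) = 56%.
- q = 0.40, t = 20%: 0.12/(0.12 + 0.16) = 43%.

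Because only one untreated patient in five is expected to be negative, even a modest treated share could make up a large part of the specificity denominator.

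**The case against.** The strongest reply is that the protocol, read as a whole, describes a diagnostic study. The title and Study Design say so. Recruitment Methods treats the in-lab sleep study and standard polysomnography as the same thing. Study Procedures lists diagnostic airflow sensors and no positive-airway-pressure flow channel. Titration and split-night studies are never mentioned. Current CPAP use may be recorded only as history, and a CPAP user can have an untreated re-evaluation. All of this stands as evidence of intent. It does not repair the criterion, because no sentence turns the intent into an eligibility rule.

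A reader might also infer that treated nights would invalidate the comparison. The documents do not support that. Ring and PSG are recorded simultaneously, so a low AHI paired with a low REI is a concordant pair. What changes is the population that the result describes.

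A reader might infer a serious loss of power as well. At 32 positives the exact one-sided power is 83.3%, but this is a trough of a saw-toothed function: it is 86.5% at 28 positives and only 93.6% at the 40 expected from 50 patients with no treated nights. The arcsine method that reproduces the plan's 35 gives 93.5% at 32, against 95.2% at 35. The count of positives is the steadier measure, and at 80 patients the margin is wide.

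**Conclusion.** The mismatch is real, and the broader wording is the one applied at screening. It is a gap in the eligibility text, not evidence that treated nights were planned. Its main consequence is for what sensitivity and specificity represent, since treated OSA patients could enter as PSG-negatives at either sample size.

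The consequence for the number of positives depends on which enrolment figure governs. If all treated nights score negative, 35 positives are lost above a treated share of 12.5% at 50 patients but only above about 45% at 80. Both t and q are assumptions, so the actual size cannot be fixed from the documents. This is a cheap improvement worth making rather than a fault that undermines the design.

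**What to change.** Bring the first inclusion criterion into line with Study Design, for example: *adults aged 18 to 80 scheduled for a diagnostic overnight in-lab PSG for suspected OSA*. Add one sentence to the Data Analysis Plan restricting the REI-AHI comparison to recording time without positive airway pressure. This governs enrolment and which recording time is analysed; it does not touch patient care.

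The cost is two sentences and a slightly smaller pool of schedulable patients. As Study Design already describes the narrower group, little intended recruitment should be lost.
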